16.3. Exploratory Efficacy

16.3.1. Exploratory Efficacy Variables & Derivations

- Change in mean sitting DBP and SBP between Visit 1 (Week -4) and Visit 2 (Week 0), Visit 3 (Week 4) and Visit 4 (Week 8):
 - In the group of patients who were on NEB 5 mg and AML 5 mg at Visit 1 (Week -4) and continued to be on the same therapies.
 - In the group of patients who switched to NEB 5 mg or AML 5 mg from any other BBs or CCBs at Visit 1 (Week -4).
- To assess change in mean sitting DBP and SBP, for uncontrolled patients at Visit 3 (Week 4), between Visit 2 (Week 0) and Visit 3 (Week 4).
- Number and proportion of patients achieving the BP goal (sitting BP < 130/80 mmHg) at Visit 2 (Week 0), Visit 3 (Week 4) and Visit 4 (Week 8):
 - In the group of patients who were on NEB 5 mg and AML 5 mg at Visit 1 (Week -4) and continued to be on the same therapies.
 - In the group of patients who switched to NEB 5 mg or AML 5 mg from any other BBs or CCBs at Visit 1 (Week -4).
- Number and proportion of patients divided into subgroups according to the hypertension grade, the presence of diabetes and/or of hypercholesterolemia achieving the BP goal (sitting BP < 130/80 mmHg) at Visit 2 (Week 0), Visit 3 (Week 4), and Visit 4 (Week 8).
 - In the group of patients who were on NEB 5 mg and AML 5 mg at Visit 1 (Week -4) and continued to be on the same therapies.
 - In the group of patients, who switched to NEB 5 mg or AML 5 mg from any other BBs or CCBs at Visit 1.

Document: \\veedc-vnasc01\Biosdata\Menarini\NebAml\ZZA67778\Biostatistics\Documentation\SAP\SAP_Menarini_MEIN21AmNe-Hyp001_Final_V1.0

Author: [name]

Version Number:

Final V1.0

Version Date:

11Nov2022

Template No.: CS_TP_BS016 Revision 7

Reference: CS_WI_BS005

Effective Date: 01Nov2021

16.3.2. Analysis of Exploratory Efficacy Variables

Exploratory efficacy variables will be summarized in a descriptive manner using ENR and mITT populations for Visits 1, 2, 3 and 4.

- Change in sitting DBP and SBP from Visit 1 (Week -4) will be using paired t-test. The p-value obtained from the paired t-test will be presented for the visits - Visit 2 (Week 0), Visit 3 (Week 4) and Visit 4 (Week 8). Assumption of Normality will be investigated using Wilk-Shapiro test. If the data is found to be non-Normal, then paired t-test will be replaced by Wilcoxon signed rank test. A descriptive summary using n, mean, median, SD, Q1, Q3, minimum, and maximum is also presented.
- Change in mean sitting DBP and SBP for uncontrolled patients between Visit 2 (Week 0) and Visit 3 (Week 4) will be using paired t-test. The p-value obtained from the paired t-test along with n, mean, median, SD, Q1, Q3, minimum, and maximum will be presented. Assumption of Normality will be investigated using Wilk-Shapiro test. If the data is found to be non-Normal, then paired t-test will be replaced by Wilcoxon signed rank test.
- The number of patients achieving BP goal (sitting BP < 130/80 mmHg) will be summarized for Visits 2, 3, and 4, along with percentage and 95% CI for the proportion. A p-value using exact McNemar's test will be presented to compare the proportion of patients achieving the BP goal (sitting BP < 130/80 mmHg) between Visit 2 and Visit 3 as well as Visit 2 and Visit 4. A p-value using McNemar's test will be presented to compare the proportion of patients achieving the BP goal (sitting BP < 130/80 mmHg) between Visit 3 and Visit 4.
- The number of patients achieving BP goal (sitting BP < 130/80 mmHg) will be summarized for Visits 2, 3 and 4, along with percentage for each of the subgroup specified under section 7.5 of the SAP.

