and AML 5 mg. Patients with controlled BP levels (sitting SBP/DBP <130/80 mmHg) and/or who do not tolerate the treatment or have an adherence range below 80% or above 120%, will be withdrawn from the study.

After 4 weeks  $\pm 2$  days in the assessment period, patients BP will be further evaluated at Visit 3: patients with controlled BP levels (sitting SBP/DBP <130/80 mmHg) will continue the same extemporaneous combination, while patients with uncontrolled BP levels will be uptitrated from extemporaneous combination NEB/AML 5/5 mg to extemporaneous combination of NEB/AML 5/10 mg for further 4 weeks.

At the end of the assessment period (8 weeks  $\pm 4$  days), the patients will attend an End of Treatment Visit 4. To correctly evaluate the additional effect of the combination therapy, the number of patients with uncontrolled BP on NEB or AML monotherapy needs to be balanced at Visit 2. In order to maintain a 1:1 ratio during the assessment period, a cap of 110 patients for each treatment arm (ie. NEB and AML) will be included at Visit 2 in order to maintain a balanced number of uncontrolled patients entering the assessment period for each drug. The evaluation will be done every 50 patients. If the rate of entrance in the assessment period for one of the 2 tested drugs will deviate more than 5%, a corrective measure will be initiated: according to the enrolment site statistics, one or more sites will be informed to enroll a greater number of patients being treated with the least represented drug in the assessment period.

A total number of 290 patients will be screened considering 25% of drop-out rate, to obtain approximately 216 completed patients at the end of the study (Visit 4).

Sitting BP will be measured at all visits before blood sampling. BP will be measured in both arms at the Screening visit (Visit 1) in order to detect possible between-arm differences. The arm with the higher mean DBP will be used in all subsequent visits for BP assessment. Blood pressure measurements should be performed as nearly as possible within the same time frame of the day (7:00 to 12:00 a.m.), on the same arm, possibly by the same member of the site staff/personnel, and using the same calibrated equipment at each visit.

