## 12.5.5 Exploratory (efficacy) analysis

Exploratory efficacy variables will be summarized in a descriptive manner using enrolled population for Visits 1, 2, 3 and 4.

• Change in mean sitting DBP and SBP between Visit 1 (Week -4) and Visit 2 (Week 0), Visit 3 (Week 4) and Visit 4 (Week 8):

MENARINI	Corporate Medical Department		
	]	rotocol Template	
Identification Number	Version Number	State	Effective date
FORM-000050125	2.0, CURRENT	Effective	08 Jan, 2021

Study Code: MEIN/21/AmNe-Hyp/001

- In the group of patients who were on NEB 5 mg and AML 5 mg at Visit 1 (Week -4) and continued to be on the same therapies.
- In the group of patients who switched to NEB 5 mg or AML 5 mg from any other BBs or CCBs at Visit 1 (Week -4).
- To assess change in mean sitting DBP and SBP, for uncontrolled patients at Visit 3 (Week 4), between Visit 2 (Week 0) and Visit 3 (Week 4).
- Number and proportion of patients achieving the BP goal (sitting BP <130/80 mmHg) at Visit 2 (Week 0), Visit 3 (Week 4) and Visit 4 (Week 8):
  - In the group of patients who were on NEB 5 mg and AML 5 mg at Visit 1 (Week -4) and continued to be on the same therapies.
  - In the group of patients who switched to NEB 5 mg or AML 5 mg from any other BBs or CCBs at Visit 1 (Week -4).
- Number and proportion of patients divided into subgroups according to the hypertension grade, the presence of diabetes and/or of hypercholesterolemia achieving the BP goal (sitting BP <130/80 mmHg) at Visit 2 (Week 0), Visit 3 (Week 4), and Visit 4 (Week 8).
  - In the group of patients who were on NEB 5 mg and AML 5 mg at Visit 1 (Week -4) and continued to be on the same therapies.
  - In the group of patients, who switched to NEB 5 mg or AML 5 mg from any other BBs or CCBs at Visit 1.

Change in sitting DBP and SBP between visits will be using paired t-test. The p-value obtained from the paired t-test will be presented. Assumption of Normality will be investigated using Wilk-Shapiro test. If the data is found to be non-Normal, the paired t-test will be replaced by Wilcoxon signed rank test.

The exploratory endpoints will also be presented in a descriptive manner using n, mean, median, SD, Q1, Q3, minimum, and maximum.

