3.3. Changes to Analysis from Protocol

- The secondary and exploratory analysis use McNemar's test to analyze proportion of patients achieving BP goal (SBP/DBP <130/80 mmHg) between visit 2, visit 3, and visit 4. As per the entry criteria to the combination therapy, only those patients with uncontrolled BP (SBP/DBP \geq 130/80 mmHg) at visit 2 are eligible. So, the proportion of patients achieving the BP goal at visit 2 will be always zero. Thus, SAP has been updated with exact McNemar's test instead of McNemar's test when comparing the counts with respect to visit 2.
- As per protocol, the definition of Per Protocol Population is "All patients included in the Safety population who do not have any major protocol deviations that could affect the analyses.". In SAP, this has been updated to,
"The Per-Protocol (PP) population will contain all patients included in the Safety population who do not have any major protocol deviations that could affect the primary efficacy analyses and have at least baseline (Week 0) and Week 8 assessments with primary efficacy data".
- As per protocol, the definition of ENR Population is "Patients who are enrolled into the study (ie. signed ICF and met the eligibility criteria) and may or may not receive the study treatment (extemporaneous combination)." In SAP, this has been updated to,
"The Enrolled (ENR) population will contain all patients who are enrolled into the study (i.e. signed ICF and met the eligibility criteria) and may or may not receive the study medication (i.e., monotherapy and/or combination therapy). An enrolled patient who does not meet the inclusion/exclusion criteria might be included in the ENR population as per the investigator discretion."
- As per protocol, Compliance to study medication will be summarized for Enrolled and Safety populations. In SAP, this has been updated to consider the summary based on SAF and mITT because Safety population will include monotherapy patients and thus analysis on ENR is not required.

Document: \\ieedc-vnasc01\Biosdata\Menarini\NebAml\ZZA67778\Biostatistics\Documentation\SAP\SAP_Menarini_MEIN21AmNe-Hyp001_Final_V1.0

Author: [name]

Version Number:

Final V1.0

Version Date:

11Nov2022

Template No.: CS_TP_BS016 Revision 7

Reference: CS_WI_BS005

Effective Date: 01Nov2021

- As per protocol, exploratory efficacy analyses will be summarized for Enrolled population. In SAP, this has been updated to include summary based on mITT population as well.

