5.1. Enrolled [ENR] Population

The Enrolled (ENR) population will contain all patients who are enrolled into the study (i.e. signed ICF and met the eligibility criteria) and may or may not receive the study medication (i.e., monotherapy and/or combination therapy). An enrolled patient who does not meet the inclusion/exclusion criteria might be included in the ENR population as per the investigator discretion.

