5.2. Modified Intent-to-Treat (mITT) Population

The Modified Intent-to-Treat (mITT) population will contain all patients who are in the Enrolled population, receive at least one dose of combination therapy, and have at least baseline and Week 8 assessments with primary efficacy data.

Document: \\eedc-vnasc01\Biosdata\Menarini\NebAml\ZZA67778\Biostatistics\Documentation\SAP\SAP_Menarini_MEIN21AmNe-Hyp001_Final_V1.0

Author: [name]

Version Number:

Final V1.0

Version Date:

11Nov2022

Template No.: CS_TP_BS016 Revision 7

Reference: CS_WI_BS005

Effective Date: 01Nov2021

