7. STATISTICAL CONSIDERATIONS

Summaries will include descriptive statistics for continuous variables (sample size [n], mean, standard deviation [SD], median, minimum and maximum) and for categorical variables (frequency [n] and percentage), unless otherwise stated in the relevant section. Percentages will be based on the number of patients within the relevant analysis population and treatment arm, or the number of patients with data available where relevant.

If the original data has N decimal places, then the summary statistics will have the following decimal places:

Minimum and maximum: N

Mean, median, Q1, Q3, confidence intervals, ratios: N + 1

SD: N + 2

Percentages will be reported to one decimal place. P-values should be reported to three decimal places, except values <1.000 but >0.999 will be presented as '>0.999' (e.g., 0.9998 is presented as >0.999); and values <0.001 will be presented as '<0.001' (e.g., 0.0009 is presented as <0.001)

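### On the Enrolled set, the exploratory Visit 2–4 goal-rate tables print a series that the p-values beside it do not test, because patients at goal at Visit 2 leave by design

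*SAP*

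**What the plan says.** - **Population for the exploratory tables.** Protocol 12.5.5: "Exploratory efficacy variables will be summarized in a descriptive manner using enrolled population for Visits 1, 2, 3 and 4". SAP 16.3.2 keeps that set and adds mITT: "Exploratory efficacy variables will be summarized in a descriptive manner using ENR and mITT populations for Visits 1, 2, 3 and 4". The goal-rate tables cover Visits 2, 3 and 4. Exact McNemar p-values are planned for Visit 2 against Visit 3 and against Visit 4, and an ordinary McNemar test for Visit 3 against Visit 4.
- **Who is in ENR.** SAP 5.1 takes all enrolled patients, who "may or may not receive the study medication (i.e., monotherapy and/or combination therapy". Starting the combination is not required.
- **Who is in mITT.** SAP 5.2 requires at least one combination dose, and patients must "have at least baseline and Week 8 assessments with primary efficacy data".
- **What happens at Visit 2.** Protocol section 5 names "Patients with controlled BP levels (sitting SBP/DBP <130/80 mmHg) and/or who do not tolerate the treatment", and those who "have an adherence range below 80% or above 120%, will be withdrawn from the study".
- **Premise for the test.** SAP 3.3 argues from the entry rule for the combination that "the proportion of patients achieving the BP goal at visit 2 will be always zero", and on that basis moves the secondary and exploratory analyses to the exact test. The protocol synopsis likewise takes every patient to be uncontrolled at Week 0.
- **Missing data and denominators.** SAP 7.3 uses observed data without imputation. SAP section 7 bases percentages on the population and arm, "or the number of patients with data available where relevant", without fixing the choice for these tables.

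**The concern.** A by-visit goal-rate table invites the reader to follow the percentage from the end of monotherapy to the end of combination treatment and to take the adjacent p-value as a test of that step. On mITT this works. On ENR the Visit 2 percentage counts patients whom the design removes at that visit, and the later percentages count other patients. The p-value then belongs to a contrast starting from zero, which the table does not display. The tables by change from Visit 1 have the same change of cohort: the Visit 1–2 mean includes patients who leave at Visit 2, and the Visit 1–3 and 1–4 means do not. At stake is the reading of exploratory outputs, including those split by continued versus switched therapy. The trial's main conclusion is not at stake.

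**Working it through.** **1. The plan's own figures.** Protocol 12.2 wants 216 completers and allows 25% for screen failure and drop-out together. 216 / (1 − 0.25) = 288, against 290 stated, so the figure is reproduced. The allowance leaves 290 − 216 = 74 patients lost between Visit 1 and Visit 4. The documents do not say how many of these would be at goal at Visit 2.

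**2. Where each number on ENR comes from.**

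| Quantity | Patients supplying it |
|---|---|
| Visit 2 numerator | At goal at Visit 2, then withdrawn |
| Visit 3 and Visit 4 numerators | Entered the combination uncontrolled |
| Pairs for Visit 2 v 3 and Visit 2 v 4 | The same entrants, all not at goal at Visit 2 |

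This assumes that the entry rule is followed and that no early-termination reading is counted as Visit 4.

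**3. The displayed Visit 2 percentage.** It equals c / N, where c is the number at goal at Visit 2 and N is the size of ENR. N cannot exceed the 290 screened. Assumed range for c:

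- c = 10: 10/290 = 3.4%
- c = 30: 30/290 = 10.3%
- c = 74 (the extreme in which every loss is a patient at goal at Visit 2): 74/290 = 25.5%

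A smaller ENR would raise the percentage for the same c. In the tested pairs the Visit 2 rate is 0/216 at plan size in each case.

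**4. The test.** The cell for patients at goal at Visit 2 but not later is empty by design. With k patients at goal at the later visit, the exact two-sided McNemar p-value is 2 × 0.5^k. This gives 0.0625 for k = 5, 0.031 for k = 6 and 1.9 × 10⁻⁶ for k = 20. The count c does not enter the formula.

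**5. How the two can disagree (assumed counts).** Take 30 of 290 at goal at Visit 2 (10.3%) and 20 of 216 at Visit 4 (9.3%, or 20/290 = 6.9% on the full ENR denominator). The printed series falls. The p-value beside it is 1.9 × 10⁻⁶ for a rise, because it compares 0 with 20 among the 216 pairs.

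**6. Mean changes from Visit 1.** If a share p of ENR leaves at Visit 2, the Visit 1–2 mean in all ENR differs from that in those who continue by p × (mean change in leavers − mean change in continuers). At p = 30/290, each 1 mmHg of gap between the two groups moves the ENR mean by 0.10 mmHg; at p = 74/290, by 0.26 mmHg. The gap is not given in the documents. Patients leaving because they are controlled are selected for low Visit 2 values, so a larger fall in them is likely, but the effect on the mean is probably modest.

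**The case against.** Several points on the other side stand.

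- The mITT tables planned alongside already give a cohort that started the combination, with a Visit 2 rate of zero by entry rule. ENR is the set that the protocol named.
- SAP 3.3 derives its zero from entry to the combination, so the sentence is correct in its own context. It goes wrong only when carried to ENR.
- Exact McNemar remains a sound choice on ENR, since the empty cell that motivates it is empty there too.
- Any paired test on observed data uses complete pairs. The table templates are not in the documents, so the final layout and denominators are not known, and the continuous summaries will print n.

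A reader might infer that the tests themselves compare different people, or are invalid. The documents do not support this: each paired t-test and McNemar test is within-patient. The change of patients is in the displayed series.

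A reader might also infer that patients withdrawn at Visit 2 cannot have a Visit 4 value. That is not established. Protocol section 10 asks early discontinuers to complete the Visit 4 assessments, while SAP 6.3 summarises nominal visits and SAP Appendix 1 lists Early Termination separately. Handling is therefore unclear. Counting such a reading as Visit 4 would not repair the table: Visit 3 would still be missing, and the value would not follow combination treatment.

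A footnote with n per visit would help, but it would leave a p-value beside percentages that it does not test.

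**Conclusion.** The point holds as a minor correction to exploratory outputs. On ENR, the Visit 2 goal percentage and the later percentages come from different patients, and the McNemar p-values relate only to those who entered the combination. The SAP 3.3 premise is true for combination starters and false for ENR whenever anyone is at goal at Visit 2. The size depends on that share, which the documents do not give; the assumed range displays as 3.4% to 25.5%, against zero in the tested pairs. The change of cohort in the mean changes is real but probably modest, and no mmHg figure can be put on it from the documents.

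It would be too strong to read this as a threat to the efficacy conclusion. The primary and secondary efficacy analyses use mITT and PP, and are unaffected. The conclusion assumes that goal means both components below the limit, that the entry rule is followed, and that readings from patients withdrawn at Visit 2 are not labelled Visit 4.

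**What to change.** 1. On ENR, report Visit 2 only: the goal rate and the Visit 1–2 change, split by patients who entered the assessment period and patients withdrawn at Visit 2.
2. Give Visit 3 and Visit 4 summaries, and all between-visit tests, only for patients who started the combination, with n at each visit.
3. State in SAP 16.3.2 that early-termination readings of patients withdrawn at Visit 2 are not counted as Visit 4.
4. Reword SAP 3.3 so that the zero at Visit 2 applies to combination starters, and list there the departure from protocol 12.4 and 12.5.5.

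The cost is revised table shells and short edits to SAP 3.3 and 16.3.2. No new data are needed. The downside is a small, documented change from the population that the protocol names for exploratory tables.

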- c. Patients on NEB 5 mg or AML 5 mg will continue the same therapy for 4 weeks (run-in period). Patients on any other BBs will be assigned to monotherapy with NEB 5 mg and the patients on other CCBs (except AML 10 mg) will be assigned to monotherapy with AML 5 mg. The allowed CCBs are: felodipine, lacidipine, lacidipine, nicardipine, nicardipine, nimodipine, and nisoldipine).
- d. Only patients with controlled BP at Visit 3 will receive NEB/AML 5/5 mg for next 4 weeks.
- e. Only patients with uncontrolled BP at Visit 3 will receive NEB/AML 5/10 mg for next 4 weeks.
- f. All concomitant medications ongoing at the time of the consent and any surgery/procedures should be reported.
- g. Pregnancy test (urine): only for females of childbearing potential.
- h. Vital signs will include body temperature, respiratory rate, and pulse rate.
- i. To ensure patient safety, the patients will be contacted over a phone call within 24 hours, in case of any abnormality and clinically relevant laboratory test according to the Investigator's judgment at any visit.

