
 
To assess change in mean sitting DBP and SBP between Visit 1 (Week -4) and Visit 2 (Week 0), Visit 3 (Week 4) and Visit 4 (Week 8):
 
In the group of patients who were on NEB 5 mg and AML 5 mg at Visit 1 and continued to be on the same therapies.
 
In the group of patients who switched to NEB 5 mg or AML 5 mg from any other BBs or CCBs at Visit 1.
 
	
 
Change in mean sitting DBP and SBP between Visit 1 (Week -4) and Visit 2 (Week 0), Visit 3 (Week 4) and Visit 4 (Week 8):
 
In the group of patients who were on NEB 5 mg and AML 5 mg at Visit 1 and continued to be on the same therapies.
 
In the group of patients who switched to NEB 5 mg or AML 5 mg from any other BBs or CCBs at Visit 1.
 
	Evaluation of the antihypertensive efficacy of combination therapy in the sub-group of patients who switched from a different BB or CCB and in the sub-group of patients who were on nebivolol or on amlodipine at the inclusion in the study.

 
To assess the change in mean sitting DBP and SBP between Visit 2 (Week 0) and Visit 3 (Week 4) for uncontrolled patients at Visit 3 (Week 4).
 
	
 
Change in mean sitting DBP and SBP for uncontrolled patients at Visit 3 (Week 4), between Visit 2 (Week 0) and Visit 3 (Week 4).
 
	To collect and analyze data not only in the overall population of patient but also in patients considered uncontrolled after 4 weeks of combined therapy.

 
To assess the antihypertensive efficacy of the extemporaneous combination of NEB 5 mg with AML 5 mg or AML 10 mg by evaluating the number of patients achieving the BP goal (sitting BP <130/80 mmHg) at Visit 2 (Week 0), Visit 3 (Week 4) and Visit 4 (Week 8):
 
In the group of patients who were on NEB 5 mg and AML 5
 
	
 
Number and proportion of patients achieving the BP goal (sitting SBP/DBP <130/80 mmHg) at Visit 2 (Week 0), Visit 3 (Week 4), and Visit 4 (Week 8):
 
In the group of patients who were on NEB 5 mg and AML 5 mg at Visit 1 (Week -4) and continued to be on the same therapies.
 
	To collect efficacy data stratifying the population of patients on the basis of the switching of the therapy.

MENARINI	Corporate Medical Department		ent
	Protocol Template		
Identification Number	Version Number	State	Effective date
FORM-000050125	2.0, CURRENT	Effective	08 Jan, 2021

OBJECTIVES	ENDPOINTS	JUSTIFICATION FOR ENDPOINTS

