### *Study Code:* MEIN/21/AmNe-Hyp/001

### 6.2.1 Inclusion Criteria

A patient will be considered eligible for inclusion in the study only if all of the following criteria are met:

- 1. Male or female patients with Grade 1 2 hypertension with mean sitting SBP ≥140 mmHg and ≤179 mmHg and/or mean sitting DBP ≥90 mmHg and ≤109 mmHg at screening (in accordance with the 2018 ESC/ESH guidelines definition), ≥18 and <65 years of age, on monotherapy treatment either with BBs or CCBs for at least 4 weeks before Visit 1 (screening).
- 2. Patients are able to understand and have freely given written informed consent at Screening Visit.
- 3. Patients who are able to comply with all study procedures and who are available for the duration of the study.
- 4. Ability to take oral medication and willing to adhere to the drug regimen.
- 5. Female patients are eligible to participate if not pregnant, or not breastfeeding and if they refrain from donating or storing eggs. For females of reproductive potential: use of highly effective contraception (eg. method of birth control throughout the study period and for 4 weeks after study completion defined as a method which results in a failure rate of <1% per year) such as:
  - Combined hormonal contraception (estrogen- and progestogen-containing) associated with inhibition of ovulation (oral, intravaginal, and transdermal).
  - Progestogen-only hormonal contraception associated with inhibition of ovulation (oral, injectable, and implantable).
  - Intrauterine device.
  - Intrauterine hormone-releasing system.
  - Bilateral tubal occlusion.
  - Vasectomized partner (procedure conducted at least 2 months before the screening), (provided the partner is the sole sexual partner of the trial patient and that the vasectomized partner has received medical assessment of the surgical success).
- 6. A male patient must agree to use contraception during the whole study period and for at least 1 week after the last dose of study treatment and refrain from donating sperms during this period.

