3. STUDY DESIGN

3.1. General Description

This is a Phase IV, interventional, open-label, multicenter, multinational study with 2 study periods (a run-in period of 4 weeks and an assessment period of 8 weeks). Patients with hypertension with systolic blood pressure (SBP) ranging from ≥ 140 to ≤ 179 mmHg and diastolic blood pressure (DBP) ranging from ≥ 90 to ≤ 109 mmHg on treatment with any beta-blockers (BBs) or calcium channel blockers (CCBs) including NEB 5 mg or AML 5 mg for at least one month prior to Visit 1 will be screened for eligibility. On the same day of the Screening visit, eligible patients will enter into a run-in period after screening, during which:

- Patients receiving NEB 5 mg or AML 5 mg will continue the same therapy for 4 weeks.
- Patients on any other BBs or CCBs will be switched to NEB 5 mg or AML 5 mg.

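### The first exploratory analysis tests BP change from Visit 1, the reading that qualified patients, so its p-values partly measure regression to the mean and its changes overstate the combination's effect

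*SAP*

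**What the plan says.** Protocol 6.2.1 admits patients with "mean sitting SBP ≥140 mmHg and ≤179 mmHg and/or mean sitting DBP ≥90 mmHg and ≤109 mmHg at screening". SAP 3.1 adds: "On the same day of the Screening visit, eligible patients will enter into a run-in period after screening". No second baseline reading is taken after a patient qualifies. Protocol section 5 measures both arms at Visit 1 and then fixes the arm: "The arm with the higher mean DBP will be used in all subsequent visits for BP assessment".

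Protocol 2.2 (note c) and SAP 3.1 keep patients already on nebivolol 5 mg or amlodipine 5 mg on that drug through run-in. Patients on another beta-blocker or calcium channel blocker are switched.

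The first bullet of SAP 16.3.2 reads: "Change in sitting DBP and SBP from Visit 1 (Week -4) will be using paired t-test". P-values are presented for Visits 2, 3 and 4, and SAP 16.3.1 lists continuers and switchers as the groups. Protocol 12.5.5 plans the same test in the Enrolled (ENR) population. SAP 3.3 extends the exploratory analyses: "In SAP, this has been updated to include summary based on mITT population as well". Protocol section 4 gives the purpose as "Evaluation of the antihypertensive efficacy of combination therapy in the sub-group of patients who switched from a different BB or CCB" and in those already on nebivolol or amlodipine.

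The other bullets of SAP 16.3.2 do not use Visit 1. They cover the change from Visit 2 to Visit 3 in uncontrolled patients, and BP-goal rates at Visits 2, 3 and 4. The primary and first secondary endpoints run from Visit 2 to Visit 4.

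**The concern.** Patients chosen because a reading was high will on average read lower next time, even if nothing is done. Here the high reading is both the entry criterion and the baseline of the test. Taking the arm that read higher that day pushes in the same direction.

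In continuers there is no new treatment between Visits 1 and 2, so a significant fall there says little about any drug. In switchers the artefact is mixed with the switch. From Visit 1 to Visits 3 and 4 it is added to whatever the combination does, in an analysis whose stated purpose is to evaluate the combination.

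The bullet can produce up to 2 groups × 2 BP components × 3 visits × 2 populations = 24 p-values. SAP 7.4 marks multiplicity as not applicable, and neither document attaches a caveat about regression to the mean.

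The mITT version has a further problem. It keeps only patients who went on to the combination, which required uncontrolled BP at Visit 2. Its Visit 1 to Visit 2 change is therefore selected on its own end value.

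**Working it through.** **Inputs.** The plan gives no operating figure for these tests. From the documents come the entry band at Visit 1, the 130/80 limit at Visit 2, two-sided 5% tests (SAP 6.5), and the sample-size inputs for DBP: SD of change 10 mmHg and planned change 4 mmHg (Protocol 12.2). The source-population mean, the visit-to-visit correlation ρ and the number of continuers are not given, so they are assumed over a range. True BP is held constant throughout. The SBP-DBP correlation is assumed to be 0.6.

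**Mechanism.** If SBP and DBP share the same ρ, the expected change is −(1 − ρ) × (mean Visit 1 value of those selected − source mean). The SD of change before selection is visit SD × √(2(1 − ρ)). A visit SD of 10 with ρ = 0.5 gives 10 × √1 = 10, which is the protocol's figure.

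**Fall needed for p<0.05** at SD 10, from t × 10/√n: 2.8 mmHg with 50 patients, 2.0 with 100 and 1.6 with 145.

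**One case in full.** Source mean 140/86, visit SD 15/10, ρ = 0.5, 'and/or' entry.
- The simulated mean Visit 1 DBP of those selected is 90.92, so the expected change is −0.5 × (90.92 − 86) = −2.46 mmHg.
- The SD of change is 9.52. With 100 continuers the standard error is 0.952, and the ratio is 2.46/0.952 = 2.58.
- Against a critical value of 1.98, the chance of a significant fall is about Φ(2.58 − 1.98) = Φ(0.60) = 73%.

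**First set of assumptions** (between-patient SD 12/7, within-visit SD 9–11/6–7, source means 138–146/86–92), ENR, Visit 1 to Visit 2:

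| Entry rule | DBP fall (mmHg) | p<0.05 with 50 continuers | p<0.05 with 145 continuers |
|---|---|---|---|
| SBP and/or DBP in band | 1.0–2.6 | 13–49% | 30–92% |
| both in band | 2.4–5.3 | 60–99% | 97–100% |

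The 145 is half of the 290 screened. It is an assumption and probably generous, since 290 includes screen failures.

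**Second, wider set** (source means 135/82, 140/86, 145/90, 150/94; visit SD 15/10; ρ 0.5 to 0.8; both entry rules; 24 scenarios).
- ENR DBP falls in all 24, by 0.2 to 7.0 mmHg.
- With 100 continuers and ρ = 0.5, the chance of a significant DBP fall for the four means in order is 94%, 73%, 35% and 8% under 'and/or' entry. If both limits apply it is about 100%, 100%, 99% and 72%.
- At the mildest corner (150/94, ρ = 0.8, 'and/or') the fall is 0.2 with SD 6.2. The ratio is 0.2/0.62 ≈ 0.3, and two-sided rejection is about 6%.

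**mITT, Visit 1 to Visit 2.** Under 'and/or' entry and the Protocol 2.1 wording that both SBP and DBP be high at Visit 2, the DBP change in the second set is −0.2 to +0.1 mmHg, with significance in 2–5%. If either component is enough at Visit 2, DBP falls by 0.5 to 2.2.

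**Visit 1 to Visit 4, no drug effect.** DBP falls by 0.2 to 6.8 mmHg in mITT in the second set, against a planned effect of 4. Adding the first set's 1.0 to 5.3 to a true −4 gives about −5 to −9.

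**Visit 2 to Visit 4, no drug effect, mITT.** The change is −2.8 to +0.7 mmHg. The worst case is smaller than from Visit 1 (2.8 against 6.8). The gain is small when entry is 'and/or' and both components must be high at Visit 2. At 135/82 with ρ = 0.5 there is none (2.8 from Visit 2, 2.7 from Visit 1).

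**The case against.** The strongest reply is that these analyses are exploratory, are called descriptive, were specified in Protocol 12.5.5, and support no decision. That limits the importance of the point. It does not answer it, because SAP 16.3.2 presents p-values all the same.

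The size also rests on inputs the documents do not give. That stands. A reader might infer that continuers are bound to show a significant fall, but the range above does not support that, and in mITT the DBP change can be near zero. Nor is the drug the only thing that could differ between Visits 1 and 2. Trough timing, fixed dosing hours and tablet counts begin with the study and may move BP either way. They were not modelled, and neither was the choice of the higher arm.

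Three stronger readings are tempting and unsupported:
- **That the primary result is affected.** It starts from Visit 2.
- **That the objective is to compare switchers with continuers.** Protocol section 4 and SAP 2.3 ask for change within each group and state no contrast. A switcher-versus-continuer ANCOVA would not reliably cancel the artefact either. With no true change and different source means (142/89 against 146/92, or 138/86 against 146/92), it gives spurious DBP differences of −1.4 and −2.8 mmHg, significant about 23% and 68% of the time with an assumed 100 per group.
- **That the continuers' Visit 1 to Visit 2 change is the drift to subtract from the primary change.** It follows selection at 140/90 in ENR; the primary change follows selection at 130/80 in mITT. In one simulation the first was −1.1 to −2.4 mmHg. The no-drug Visit 2 to Visit 4 change was −0.4 to +0.1 if either component counts as uncontrolled, and −0.6 to −1.6 if both must.

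**Conclusion.** The point holds for the first bullet of SAP 16.3.2 and for nothing wider. Visit 1 is both the selecting reading and the baseline, so the Visit 1 to Visit 2 test in continuers mainly reflects regression to the mean and visit effects. Visit 1 to Visit 3 or 4 overstates the combination.

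The direction is firm: ENR DBP falls in every scenario tried with no true change. The size is not. It is about 1 to 5 mmHg under the first set of assumptions and 0.2 to 7.0 under the wider one. False-positive rates run from close to nominal at the mildest corner, through 13% at the low end of the first set, to nearly 100%. They depend on the source mean, the visit-to-visit correlation, the number of continuers and the reading of the entry rule.

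The primary and first secondary endpoints are outside this point. It is worth acting on because the change is nearly free.

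**What to change.** In SAP 16.3.2, with Protocol 12.5.5 aligned and the change listed in SAP 3.3:

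- (a) Present changes from Visit 1 as means with 95% confidence intervals and no p-values. Put a regression-to-the-mean caveat on the table itself, since an interval that excludes zero invites the same misreading.
- (b) Drop Visit 1 to Visit 2 in mITT. Later visits can stay, since mITT holds a nearly fixed set of patients.
- (c) Assess the combination by prior-therapy group from Visit 2 (to Visit 3 and to Visit 4). State that this baseline generally reduces the bias but does not remove it, because patients are also selected on BP at Visit 2.
- (d) Do not offer the continuers' Visit 1 to Visit 2 change as a quantity to subtract from the primary change. If a switcher-versus-continuer ANCOVA is added, label it optional, non-randomised and open to the same artefact when the groups come from different BP distributions.

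The passages that set the size of the bias should also be reconciled. Entry is worded 'and/or' in Protocol 6.2.1 but 'and' in SAP 3.1, and Protocol 2.1 words uncontrolled BP differently from Protocol section 5.

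The cost is SAP and protocol wording and a few table shells, with no new data. The loss is the Visit 1-based exploratory p-values that the protocol had specified.
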